12. STATISTICAL ANALYSIS

- *Describe how your data will be used to test the hypotheses.*
- *State clearly what variables will be tested and what statistical tests will be used.*
- *Include sample size calculations.*
- *If this is a pilot study, state which variables will be examined for hypothesis generation in later studies.*

The sample size of 60 participants was chosen to have a sufficient number of patients to obtain a preliminary assessment of the feasibility of personalized trials of sleep quality with melatonin compared to a placebo. The numbers of sleep quality reports, questionnaires, and intervention repetitions per trial were based on expert recommendations by a statistician and estimations about maximal duration of the trial to maintain patient engagement. With n=60 randomized participants, expecting a trial completion rate of 70%, we anticipate SUS data are available in

about $n = 42$ participants, thus giving a standard error no greater than 8% in estimating the rate of SUS $\geq 85^{22}$. The standard error will be the largest when the trial completion rate is at 50%. Data will be reported transparently so that individual level heterogeneity can be assessed²³.

Participants will be randomized into one of two different intervention orders, ABCCBA or CBAABC, where A=3mg dose melatonin, B=.5mg dose melatonin, and C=placebo. Although participants will be aware of their randomization order (i.e. 'A' weeks, 'B' weeks, and 'C' weeks), they will be blinded to each letter's corresponding supplement or placebo until their participant summary report. Two intervention orders were chosen to test out the feasibility of carrying out a virtual, N-of-1 study. ABCCBA was chosen as an order to test participant acceptability with back-to-back single-blinded placebo intervention (i.e., no intervention) extending through 4 weeks. CBAABC was chosen as a companion intervention order to ABCCBA to test participant acceptability with starting a Personalized Trial with a single-blinded placebo after a baseline run-in (i.e., no intervention for the first 4 weeks). Intervention order was not included as a factor in the statistical analysis because this is an acceptability and feasibility study.

The randomization schedule will be set up by a member of the Institute of Health System Science data team and provided to the data analyst assigned to Personalized Trials to Improve Sleep Quality. Randomization will occur with a fixed seed value for the purposes of repeatability and auditability, and the list of 60 participants will be split into two groups of 30 using a random shuffle function that takes that seed as input. The order in which an individual becomes eligible for one of these 60 randomizations will determine the placement given (i.e. the first person eligible will be randomized to the intervention order given to participant 1, and continue sequentially). Eligibility is obtained by a participant maintaining at least 80% adherence of survey response, Fitbit wear ≥ 12 hours a day 80% of days, and 80% sleep data ≥ 180 minutes available through the baseline run-in period. The data analyst will alert the research coordinator of the assigned randomization once a participant becomes eligible during the baseline run-in period. As this pilot is not blinded to study coordinators, this concealed allocation involving the data analyst alerting the study coordinator of intervention assignment will be used to prevent bias by blinding the sequence up until time of randomization.

The primary outcome measure will be a mean usability score, obtained using the System Usability Scale (SUS), a validated 10-item questionnaire originally developed by John Brooke in 1986 that asks users to score each item on a Likert scale from Strongly Disagree (rating of 1) to Strongly Agree (rating of 5). The SUS will be presented to the participant as addressing the ease of use, complexity, consistency of the Personalized Trials system as a whole, from recruitment to receipt of the report. Individual results are calculated to arrive at a composite measure out of 100. Participant SUS scores will be averaged together. Higher scored values correlate to a more usable system, and therefore a better outcome.

Other secondary outcome measures which assess the feasibility of the Personalized Trials framework include:

- Mean participant satisfaction with Personalized Trials components supplemental to the SUS,
- Qualitative satisfaction data collected during the virtual participant follow-up interview,
- Mean participant survey adherence rate, defined as completion of each assigned survey
- Mean participant Fitbit adherence rate, defined as recorded heart rate data for \geq 12 hours each day,
- Mean participant Fitbit sleep rate, defined as recorded sleep and wake cycles
- Mean participant melatonin adherence rate, defined as retraction of the appropriate pill from adherence device on assigned nights
- Mean participant placebo adherence rate, defined as retraction of the appropriate pill from adherence device on assigned nights

In order to share a summary report of observed trends back to the participant to assess acceptability and satisfaction with the participant report, additional secondary outcomes will be analyzed on an N-of-1 level including:

- Mean Within-Subject Difference in self-reported symptoms of sleep disturbance using the Insomnia Severity Index (ISI) during 3 treatment periods from Mean Baseline
- Mean Within-Subject Difference in self-reported sleep quality using a modified version of the Consensus Sleep Diary during 3 Treatment Periods from Mean Baseline
- Mean Within-Subject Difference in Ecological Momentary Assessment Three-Times-Daily of Pain During 3 Treatment Periods from Mean Baseline, using the Numeric Pain Rating Scale adapted from McCaffery, Beebe et al. 1989
- Mean Within-Subject Difference in Ecological Momentary Assessment Three-Times-Daily of Fatigue During 3 Treatment Periods from Mean Baseline, using the Numeric Pain Rating Scale adapted from McCaffery, Beebe et al. 1989
- Mean Within-Subject Difference in Ecological Momentary Assessment Three-Times-Daily of Concentration During 3 Treatment Periods from Mean Baseline, using the Numeric Pain Rating Scale adapted from McCaffery, Beebe et al. 1989
- Mean Within-Subject Difference in Ecological Momentary Assessment Three-Times-Daily of Confidence During 3 Treatment Periods from Mean Baseline, using the Numeric Pain Rating Scale adapted from McCaffery, Beebe et al. 1989
- Mean Within-Subject Difference in Ecological Momentary Assessment Three-Times-Daily of Mood During 3 Treatment Periods from Mean

Baseline, using the Numeric Pain Rating Scale adapted from McCaffery, Beebe et al. 1989

- Mean Within-Subject Difference in Ecological Momentary Assessment Three-Times-Daily of Stress During 3 Treatment Periods from Mean Baseline, using the Numeric Pain Rating Scale adapted from McCaffery, Beebe et al. 1989
- Mean Within-Subject Difference in Self-Reported Side Effects from Baseline, using the average number of days side effects were reported during treatment periods.
- Mean Within-Subject Difference in Device-Recorded Daily Steps from Mean Baseline, using participant Fitbit data
- Mean Within-Subject Difference in Device-Recorded Nightly Sleep from Mean Baseline, using participant Fitbit data

Other exploratory analyses include:

- Google and social media ad metrics
- Social media activity, including but not limited to:
 - Social media conversion rate, defined as total impressions compared to total click-through
 - Cost per social media conversion
- Website activity, including but not limited to:
 - Total number of website visits per traffic source
 - Website bounce rates

Mean user total time on website

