10. ENDPOINTS

- *Describe the primary and secondary study endpoints*
- *Describe any primary or secondary safety endpoints*

This study is a feasibility pilot whose primary objective is to assess the acceptability, scalability of implementation, and participant satisfaction with a personalized trial methodology to resolve a chronic complaint. Thus, the primary endpoint is the system usability scale (SUS) $\geq 85^{22}$.

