Partial withdrawal, defined as study participation and data collection without the use of one of the melatonin/placebo supplements will be allowed if a participant experiences an adverse event to one of the intervention options (3mg dose melatonin, 0.5mg dose melatonin, or placebo). In instances where participants contact the research team to self-report serious side-effects or otherwise contact the research team with concerns about their self-reported side effects, participants will be permitted to continue their involvement in the study, should they be interested. Participant data will continue to be collected and monitored, while removing the self-reported adverse intervention option from their randomized protocol (i.e. skip the intervention days and continue with placebo and/or other intervention). This will allow the participant to still evaluate their individual response to the self-reported non-aggravating intervention option. In the event that both intervention options create self-reported adverse events for the participant, they will be withdrawn from the study.]

Participants who are deemed ineligible and removed from the study during the intervention period (but not the baseline period) and participants who are withdrawn from the study will still be asked to complete the end-of-study satisfaction survey and follow-up interview. These participants will not receive a personalized participant report, and therefore the questions asked in the satisfaction survey and follow-up interview will be abbreviated (will not include the approved questions about the participant report asked of other participants).

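### Does naming the trial completion rate, instead of the rate of SUS scores of at least 85, as the source of the largest standard error undermine the sample-size statement?

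*Combined protocol and SAP*

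**What the plan says.** The sample-size paragraph of Section 12 (Statistical Analysis) makes three linked statements.

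- It starts from the number randomized and the expected retention: "With n=60 randomized participants, expecting a trial completion rate of 70%, we anticipate SUS data are available in" about 42 participants.
- It draws the precision from that number: "thus giving a standard error no greater than 8% in estimating the rate of SUS" of at least 85.
- It names the worst case: "The standard error will be the largest when the trial completion rate is at 50" percent.

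Two other places bear on which quantity is meant. Section 10 (Endpoints) sets the target as a threshold on the scale: "Thus, the primary endpoint is the system usability scale (SUS" of 85 or more. Later in Section 12 the primary outcome is described as an average: "The primary outcome measure will be a mean usability score, obtained using the System Usability Scale (SUS". The precision statement concerns the first of these, the proportion reaching 85.

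**The concern.** The third statement attaches the 50% to the wrong proportion. The completion rate has already been used to turn 60 randomized into 42 with data. After that step, the quantity being estimated is the share of respondents who score at least 85, and it is that share which makes a binomial standard error largest at 50%.

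The literal wording also clashes with the sentence before it. If completion really were 50%, there would be 30 respondents, not 42, and the standard error could exceed 8%. Lower completion would make it larger still, so 50% completion is not a worst case of any kind.

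This paragraph holds the only numerical support for enrolling 60. A false statement there raises two questions: whether the 8% was computed correctly, and whether a reader might think it already allows for half the participants being lost.

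**Working it through.** **Inputs**, all from Section 12: 60 randomized; 70% expected completion; about 42 with SUS data; standard error no greater than 8%; 50% named as the worst case.

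**Step 1: the plan's own figures.** Respondents: 60 × 0.70 = 42. For a proportion p estimated from n respondents, SE = sqrt(p(1 − p)/n). This is largest at p = 0.5, which gives sqrt(0.25/42) = 7.72%. Dividing by n − 1 instead gives sqrt(0.25/41) = 7.81%. Either agrees with a bound of 8%.

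**Step 2: the standard error by SUS rate, with 42 respondents.**

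| Rate of SUS ≥ 85 | SE |
|---|---|
| 50% | 7.72% |
| 70% | 7.07% |
| 90% | 4.63% |

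The bound holds at every rate, and the maximum is at a SUS rate of 50%.

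**Step 3: the literal reading, with completion varied.** Here completion sets n, and the largest possible SE is sqrt(0.25/n).

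| Completion | n | Largest SE |
|---|---|---|
| 70% | 42 | 7.72% |
| 50% | 30 | 9.13% |
| 40% | 24 | 10.21% |
| 30% | 18 | 11.79% |

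The figure rises steadily as completion falls. It has no peak at 50%, and at 50% it is above 8%.

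**Step 4: another reading, the standard error of the completion rate itself.** With all 60 in the denominator it is sqrt(0.25/60) = 6.45% at 50% completion and sqrt(0.21/60) = 5.92% at 70%. It does peak at 50%, but neither value is the source of 8%, and the preceding sentence is about the SUS rate.

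**Step 5: how far the bound stretches.** For SE ≤ 8% at every SUS rate, n must be at least 0.25/0.08² = 39.06, so 40 respondents (7.91%); 39 gives 8.01%. With 30 respondents, 8% is still met when p(1 − p) ≤ 0.08² × 30 = 0.192, that is, when the SUS rate is at most about 26% or at least about 74%.

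Only the reading in Step 1 reproduces the stated figure. The calculation used the right proportion and the sentence misnamed it.

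**The case for a change.** The best case for acting is that the sentence is false as it stands, that it sits in the only quantitative justification for the sample size, and that it could lead a reader to believe 8% holds even at half completion. The margin is thin: 42 respondents are expected and 40 are needed for the bound to hold at every SUS rate. Someone planning the follow-on trial could misjudge how much attrition the figure tolerates.

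Much of this stands. On its natural reading the sentence is wrong, and nothing elsewhere in the document corrects it. One might say that, taken alone, it is true of an estimated completion rate. That reading cannot be excluded outright, but it is unlikely, because the standard error has just been defined for the SUS rate and completion is not listed among the outcomes.

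The consequence does not follow. The plan ties the 8% openly to about 42 respondents, so it makes no promise of 8% at 30. The threshold of 40 is also finer than the statement it would police: the plan says about 42 and gives a whole-number percentage, and 39 respondents miss by 0.01 percentage points. Respondents may not equal completers either, since under Section 16 "participants who are withdrawn from the study will still be asked to complete the end-of-study satisfaction survey and follow-up interview". The documents do not settle whether that shortened survey contains the SUS.

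Section 12 also makes a mean score the primary outcome, while the precision statement is for a proportion. That is a separate matter. The paragraph already says which quantity its standard error describes.

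**Conclusion.** A clerical slip with no effect on the trial. The intended sentence is that the standard error is largest when the rate of SUS scores of at least 85 is 50%. On that reading the maximum is 7.7% with 42 respondents, within the stated 8%. The 60 randomized, the 42 expected and the bound are all correct.

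Nothing done to participants or data depends on the sentence. The plan states no success criterion, stopping rule or test that uses this standard error, and analysts will compute it from the observed rate and the observed number of respondents. A statistician reading the paragraph would supply the right proportion from the sentence before.

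This rests on two assumptions: that the standard error is the ordinary binomial one, and that about 42 people return the SUS. If only 30 did, the standard error could reach 9.1%. That would be a result of attrition and would show in the reported precision; it is not caused by the misnamed rate.

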Ten days into the baseline period, a Consenting Coordinator will review individual adherence to Fitbit wear and to survey responses. Adherence to Fitbit wear will be defined as recorded activity of greater than 12 hours a day, and recorded sleeping activity greater than 180 minutes in total. Survey adherence will be defined as submission of a given survey. Baseline participants who do not achieve at least 80% adherence of Fitbit wear and survey submission during the first 10 days of the baseline period will be given until day 14 of the trial to obtain 80% adherence. Those who still do not meet 80% adherence by day 14 will be withdrawn from the study. Those participants who do maintain at least 80% adherence during the baseline period will be randomized to one of two intervention sequences in the pilot study. Participants who are randomized to receive intervention sequences will receive confirmation including their protocol timeline. Participants will also receive a second mailed kit including medication adherence devices containing pills of a 3mg dose melatonin, pills of a 0.5mg dose melatonin, and pills of a placebo. Participants will not know when they are taking 3 mg melatonin, 0.5 mg melatonin or placebo (single blinded). Enrollment will continue until up to 60 participants have been randomized overall, with 30 participants randomized to receive ABCCBA and 30 participants randomized to receive CBAABC.

Each intervention sequence is made up of 6 2-week periods assigning either 3mg dose melatonin, 0.5mg dose melatonin, or placebo. Participants will not be aware of which pill they are taking in assigned intervention weeks. Instead, they will receive a text notification each night asking them to take one pill out of a designated container (A, B, or C) 1 hour before bed. Melatonin or placebo will be tracked remotely through electronic adherence pill bottles that record each event of a pill being removed via a cellular connection to a de-identified dashboard. Throughout each intervention sequence, participants will be asked to refrain from taking additional melatonin on their own.

Melatonin and placebo supplements will be stored at the study team office from delivery until time of dispensation to participants upon their randomization into the intervention period. The supplements will be handled only by study personnel and stored according to labeling. Records of the batch numbers of supplements provided to each participant will be maintained.

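### Each treatment order is justified by its own placebo-placement acceptability question, but no summary by order or placebo placement is planned

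*Combined protocol and SAP*

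**What the plan says.** Section 12 gives a general reason for using two orders, the feasibility of a virtual N-of-1 study, and then a specific reason for each. On the first: "ABCCBA was chosen as an order to test participant acceptability with back-to-back single-blinded placebo intervention", lasting four weeks. On the second: "CBAABC was chosen as a companion intervention order to ABCCBA to test participant acceptability with starting a Personalized Trial with a single-blinded placebo", which together with the run-in makes four weeks without active treatment. The paragraph closes: "Intervention order was not included as a factor in the statistical analysis because this is an acceptability and feasibility study".

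The outcomes follow in the same section. For the primary outcome, "Participant SUS scores will be averaged together", and the scale is presented as rating the "Personalized Trials system as a whole, from recruitment to receipt of the report". Secondary feasibility outcomes include mean satisfaction, "Qualitative satisfaction data collected during the virtual participant follow-up interview", and "Mean participant placebo adherence rate, defined as retraction of the appropriate pill from adherence device on assigned nights". No split by order, period or placement is stated for any of them.

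Section 11 (Research Procedures) provides for "electronic adherence pill bottles that record each event of a pill being removed via a cellular connection", so adherence will be available night by night. Sections 8 and 11 put 30 participants in each order.

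**The concern.** The reason for leaving order out conflicts with the reason for having the orders. If the study is about acceptability, and each order exists to test acceptability of a particular placebo placement, acceptability is a reason to describe results by order.

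Placebo is not a side issue. Section 2 lists the feasibility of using a placebo among the pilot's purposes, and goal 4 in Section 4 is to learn participants' attitudes to a placebo arm. A later trial would want to know whether a long placebo stretch, or a placebo start, puts participants off. Followed as written, the plan reports one figure per measure across both orders, and a problem confined to one placement could be diluted in it. Even if the pooled figure did fall, it could not show which placement was responsible.

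**Working it through.** **1. The plan's own precision figure.** Inputs from Section 12: 60 randomised, 70% completion. Expected number with SUS data: 60 × 0.70 = 42. The standard error of a proportion is √(p(1−p)/n), largest at p = 0.5: √(0.25/42) = 0.077, or 7.7 points. This agrees with the stated ceiling of 8%, and it applies to the pooled sample.

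**2. Purposes set against planned outputs (Sections 10 and 12).**

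| Planned output | Level of summary | Addresses placement? |
|---|---|---|
| Mean SUS; SUS≥85 rate | All participants | No; rates the whole system |
| Mean satisfaction | All participants | No split stated; items not in the documents |
| Interviews | Qualitative | No split stated; items not in the documents |
| Survey, Fitbit wear and Fitbit sleep rates | All participants | No |
| Melatonin and placebo adherence | By treatment | Not by order or period |
| Within-subject differences from baseline | By treatment, for the participant's report | No |
| Advertising and website metrics | Recruitment | No |

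No row gives a planned summary for either placement question.

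**3. What a summary by order could deliver.** Assume equal 70% completion in the two orders: 30 × 0.70 = 21 each.
- SUS≥85 rate within one order: maximum SE √(0.25/21) = 0.109, or 10.9 points; 95% half-width 1.96 × 10.9 ≈ 21 points.
- Difference between orders: maximum SE √(2 × 0.25/21) = 0.154, or 15.4 points; half-width about 30 points.

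Description is feasible. A between-order comparison would tell very little.

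**4. Illustration of dilution.** The placebo adherence outcome is a mean of participant rates. Assume full completion. Each participant then has two placebo periods of equal length, and each period carries half of that participant's rate.
- CBAABC period 1: 30 × 0.5/60 = 25% of the pooled rate. Period 6 carries another 25%.
- ABCCBA periods 3 and 4 together: 30 × 1/60 = 50%.
- An assumed 20-point drop confined to CBAABC period 1 moves the pooled rate by 0.25 × 20 = 5 points. Confined to ABCCBA periods 3 and 4, it moves it by 0.50 × 20 = 10 points.

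The documents give no standard deviation for adherence. Assuming 15 to 30 points between participants, the 95% half-width t × SD/√n is 3.9 to 7.7 points for the pooled mean (n = 60) and 5.6 to 11.2 points for one order (n = 30). A 5-point shift is therefore about the size of the pooled uncertainty. A drop in CBAABC period 1 can be recognised as a drop only against a reference, and the one within that order is period 6.

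**The case against.** The strongest reply has four parts.

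- **The omission is disclosed, and this is a pilot.** What is left out is order as a factor in the analysis, and no between-order test is needed. That stands, and none is requested. The reason given for the omission still conflicts with the rationale for the orders.
- **The questions may be covered elsewhere.** The satisfaction survey and interview come after the report (Section 11), and the blind is kept until the report (Section 12), so completers can comment knowing which bottle was placebo. Section 12 also promises transparent reporting so that individual heterogeneity can be assessed. A reader might infer from the missing split that the placement questions will go wholly unaddressed. The documents do not support that: the survey and interview items are not included, and individual-level reporting would permit a later split. They support only that no such summary is planned.
- **Adherence is an indirect measure.** Participants do not know which pill they are taking, so a missed pill is not an opinion about placebo. Placement is also mixed with time on study: placebo falls in intervention weeks 5–8 in ABCCBA and in weeks 1–2 and 11–12 in CBAABC. It is mixed too with where the 3 mg periods fall. This stands and belongs in the text as a caveat.
- **The dilution figures rest on assumptions.** The 20-point drop, the standard deviations and full completion are all assumed. This stands. The figures show what pooling could do, and nothing in the documents makes such a drop likely.

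**Conclusion.** The point holds as a mismatch between a stated design purpose and the planned analysis. Two placement-specific acceptability questions justify the two orders, and no summary by order or placement is planned. It is worth correcting because the data will be collected anyway, but it does not threaten the trial.

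Two stronger inferences should be resisted. The first is that the primary result is compromised: the SUS rates the whole system and is pooled by design, so that result is unaffected. The second is that pooled adherence will conceal a problem: the 5-point shift follows from the 25% weight at full completion and an assumed 20-point drop, and is an illustration only. The precision figures assume 21 participants with SUS data per order, which the plan does not state.

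**What to change.** Replace the closing sentence of the paragraph on intervention orders in Section 12 with:

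> Order will not be tested. SUS, satisfaction, interview themes, completion and withdrawal (full and partial), and melatonin and placebo adherence will also be summarised descriptively within each randomised order, with 95% confidence intervals for quantitative measures. Placebo adherence and withdrawals will be shown by period (ABCCBA periods 3 and 4; CBAABC periods 1 and 6).

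Use the same SUS population by order as for the pooled SUS, and show results for withdrawn participants alongside rather than dropping them. Add three caveats:
- intervals will be wide, with an SE of the SUS≥85 rate up to about 10.9 points at an assumed 21 per order;
- placement is mixed with time on study and with the position of the 3 mg periods;
- adherence under blinding measures acceptability only indirectly.

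If these summaries are not wanted, remove the placement-specific rationale and keep the general reason for having two orders.

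The cost is a few extra, imprecise descriptive table columns from data already collected. Conduct, sample size and the primary SUS analysis do not change.

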4. OBJECTIVE(S)/SPECIFIC AIMS AND HYPOTHESES

- *A concise statement of the goal(s) of the current study.*
- *The rationale for and specific objectives of the study.*
- *The goals and the hypothesis to be tested should be stated.*

We believe the delivery of N-of-1 methodology through Personalized Trials is feasible to scale to a large, randomized trial, and eventually to standard clinical practice. In order to demonstrate this feasibility, we must be able to collect data

illustrating that Personalized Trials can be a low-burden, satisfactory tool that can be scaled to individuals and clinicians.

We will additionally examine the novel individual-level heterogeneity of intervention effect and observed outcomes made possible by the N-of-1 trial design and will test the feasibility of pooling real-world N-of-1 results across patients to efficiently estimate the observed effect of non-prescription dietary supplements for poor sleep quality and thus the N-of-1 trial design.

Thus, the goals of this pilot study are to:

1. Conduct a pilot test (N=60) of a Personalized Trial that is delivered remotely to participants in the United States.
2. Collect data regarding minimum viable product (MVP) specifications for a future technology platform to deliver Personalized Trials.
3. Incorporate medication adherence device technology into an N-of-1 platform.
4. Elicit participant attitudes and opinions toward participating in a single-blinded protocol with use of a placebo arm in their Personalized Trial
5. Elicit participant attitudes and opinions toward using Personalized Trials to help inform their personal wellness strategy.

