8. NUMBER OF SUBJECTS

- *Indicate the total number of subjects to be accrued locally. If applicable, distinguish between the number of subjects who are expected to be pre-screened, enrolled (consent obtained), randomized and complete the research procedures.*
- *If your study includes different cohorts, include the total number of subjects in each cohort.*
- *If this is multisite study, include total number of subjects across all sites.*

Up to 500 potential participants will be invited to enroll. Up to 60 participants will be randomized to complete research procedures.

Of those participants who receive randomized intervention schedules, 30 participants will be randomized to receive the study protocol in the following order of two-week intervention periods: 3 mg Dose Melatonin, .5 mg Dose Melatonin, Placebo, Placebo, .5 mg Dose Melatonin, 3 mg Dose Melatonin (ABCCBA). The remaining 30 participants will be randomized to receive the study protocol in the following order of two-week intervention periods: Placebo, .5 mg Dose Melatonin, 3 mg Dose Melatonin, 3 mg Dose Melatonin, .5 mg Dose Melatonin, Placebo (CBAABC).

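### Leaving intervention order out of the analysis suits the SUS outcome but not the pooling and heterogeneity aims: some shared time trends shift the 3 mg minus placebo difference in opposite directions in the two orders

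*Combined protocol and SAP*

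**What the plan says.** Section 12 (Statistical Analysis) randomises participants to "ABCCBA or CBAABC, where A=3mg dose melatonin, B=.5mg dose melatonin, and C=placebo". Section 11 (Research Procedures) adds: "Each intervention sequence is made up of 6 2-week periods". It plans "30 participants randomized to receive ABCCBA and 30 participants randomized to receive CBAABC". Section 12 then says: "Intervention order was not included as a factor in the statistical analysis because this is an acceptability and feasibility study". Nowhere does Section 12 name a period, trend or carryover term that could stand in for order.

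The primary outcome is the System Usability Scale (SUS). The secondary list has within-subject changes from baseline in sleep, symptom and device measures during the three treatments, to be analysed for each participant.

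Two other statements go beyond usability. Section 4 (Objectives) says that the study "will test the feasibility of pooling real-world N-of-1 results across patients to efficiently estimate the observed effect" of supplements for poor sleep. Section 12 says: "Data will be reported transparently so that individual level heterogeneity can be assessed". Section 19 (Potential Benefit) also expects pooled data to inform on melatonin's effectiveness.

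On completion, Section 12 plans for 60 randomised, "expecting a trial completion rate of 70" per cent, and so about 42 with SUS data. No figure is given by order.

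**The concern.** The participant is randomised to an order, and the order fixes where 3 mg and placebo fall in time. The two layouts mirror each other, so a time trend common to everyone can push the 3 mg minus placebo difference up in one order and down in the other. If all individual differences are put together without regard to order, that push is counted as variation between people. Section 3 hopes that such trials will help to tell melatonin responders from non-responders, and this artefact could be mistaken for part of that difference. It also makes the pooled estimate less precise and, if the orders finish with different numbers, moves it. The feasibility reason given in Section 12 does not address this, because pooling and heterogeneity are among the things whose feasibility is being tested.

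**Working it through.** **The plan's own figure.** 60 × 0.70 = 42, and sqrt(0.5 × 0.5 / 42) = 7.7%, within the stated 8%. This concerns SUS; the plan gives no precision figure for a treatment contrast.

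**Algebra.** Let p1 to p6 be the period effects shared by all participants, d the true 3 mg minus placebo effect, and P = (p1 + p6)/2 - (p3 + p4)/2.
- ABCCBA: 3 mg in periods 1 and 6, placebo in 3 and 4, so a person's difference estimates d + P.
- CBAABC: the reverse, so it estimates d - P.
- Baseline cancels, since the difference is one change from baseline minus another.

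**Which trends matter.** A linear trend gives P = 0. So does a cubic centred on the midpoint (3.5), or any curve antisymmetric about it. A quadratic q(t - 3.5)² gives +6q and -6q. A change confined to period 1 gives +0.5 and -0.5 of its size.

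**Consequences.** With n1 and n2 completers:
- false gap between the two order means: 2P;
- variance of individual differences, orders ignored: about SD² + P²;
- bias of the pooled mean: P(n1 - n2)/(n1 + n2), which is zero when n1 = n2.

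**Assumptions for size (none are in the documents).** Period-level within-person SD of 3 ISI points, independent between periods, gives an SD of sqrt(9/2 + 9/2) = 3 for a two-period mean minus a two-period mean. The shared ISI improvement is 4 points and halves its remaining distance each period.
- None has occurred by the first treatment ISI: changes 0, -2, -3, -3.5, -3.75, -3.875. P = -1.9375 + 3.25 = 1.31.
- It starts at randomisation: changes -2, -3, -3.5, -3.75, -3.875, -3.9375. P = -2.96875 + 3.625 = 0.66.

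| Quantity | P = 0.66 | P = 1.31 |
|---|---|---|
| Gap between orders, 2P (points) | 1.31 | 2.63 |
| SD ignoring order, sqrt(9 + P²) | 3.07 | 3.27 |
| 3 mg looks better with no drug effect, ABCCBA / CBAABC | 41% / 59% | 33% / 67% |
| Power loss at 21/21, from 80% | about 1.3 points | about 5.5 points |
| Size of bias at 24/18, P × 6/42 (points) | 0.09 | 0.19 |
| False positives at 26/16, nominal 5% | about 5.5% | about 7.5% |

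The third row is Φ(-P/3) and Φ(P/3). Power and false-positive rates are simulated for a true effect of 1.33 points. They compare a one-sample t test that ignores order with the average of the two order means (pooled within-order variance, n - 2 degrees of freedom). Ignoring order does not inflate false positives at 21/21 or 24/18.

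The bias can go either way. At P = 1.31, the 24/18 split gives a rejection rate of about 60% ignoring order against 79% using it; the 18/24 split gives about 85% against 79%.

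**Range.** P scales with the size of the improvement: 0.33 to 0.66 for 2 points and 0.98 to 1.97 for 6 points. The added variance P²/SD² then runs from 1% to 43% at SD 3, and from 0.4% to 16% at SD 5.

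**How likely is imbalance?** If 42 of 60 complete regardless of order, a split of 24/18 or more uneven has a probability of about 16%, and 26/16 or more uneven about 1%.

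**The case against.** The strongest reply is that the plan contains no pooled 3 mg minus placebo test, alpha or power. The listed outcomes are changes from baseline, analysed for each person to build reports, and Section 23 says that the study is not designed to document benefit. This stands in part: the power and false-positive figures describe an analysis that the plan implies but does not define. It does not remove the point, because pooling and heterogeneity are stated aims, and the only rule given for them is to leave order out.

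A reader might infer more than the documents support:
- *Any curved trend does harm.* Curves antisymmetric about the midpoint cancel.
- *The pooled effect is biased.* Only with unequal completer numbers, and then in either direction. Section 12 chose the orders to test acceptability of different placebo placements, so unequal completion is plausible, but no figure supports it. The 42 counts participants with SUS data; Section 16 keeps sleep data up to voluntary withdrawal, so the numbers for those outcomes may differ.
- *False positives are inflated.* In these scenarios only near 26/16, which is rare if completion is unrelated to order.
- *Participants would visibly split into responders and non-responders.* Even at P = 1.31 the two order means are 2.63/3 = 0.87 SD apart, too close to show two clear groups.
- *The larger P is the natural value.* It needs no improvement at all by the first treatment ISI, which Section 11 collects at the end of a two-week period.

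**Conclusion.** The point holds in limited form. The mirror-image layout and the omission of order are certain from the text. Given a shared trend with P not equal to zero, the false gap between orders and the loss of precision follow even with equal completion; bias of the pooled mean needs unequal completion as well. The size is unknown. Under the 4-point, SD 3 assumptions it is modest: 1.3 to 5.5 points of power at 21/21, and 0.09 to 0.19 ISI points of bias at 24/18. The primary SUS outcome is untouched. The change is worth making because it analyses participants by the groups to which they were randomised, at almost no cost, and not because a large error has been shown.

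**What to change.** Limit the Section 12 sentence on order to the SUS and acceptability outcomes, and add:

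> *For any pooled 3 mg minus placebo estimate of the sleep, symptom and device outcomes, the effect is the unweighted average of the two order-specific mean within-person differences, with the standard error from the pooled within-order variance; between-person spread is computed around the order-specific means, and individual differences are displayed by order.*

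Averaging the order means gives ((d + P) + (d - P))/2 = d whatever the completer split, and holds the false-positive rate at 5% in the simulations. The analysis must work on per-person differences, or fit period effects. An order main effect added to a period-level model that already has participant effects would not help.

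The algebra assumes that all four 3 mg and placebo periods are observed, so the plan should also say how people with missing periods enter.

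**What it does not reach.** Single-participant reports cannot be corrected this way, because within one person a quadratic period trend is fully aliased with treatment. Changes from baseline still carry the time trend. Contrasts with 0.5 mg, which sits in periods 2 and 5 in both orders, are a separate matter.

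**Cost.** One sentence, a grouping variable already recorded, and one degree of freedom. If drift is purely linear and completion unequal (24/18 to 26/16), about 1 to 2.5 percentage points of power are lost. No new data, participants or procedures are needed.
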